#### Inclusion criteria

- 1) Married or considers themselves married
- 2) Living with partner most of the time
- 3) Living within the selected villages in the last 3 months
- 4) Age 18 (or an emancipated minor) to 40 for women; age 18 to 50 for men
- 5) Luganda speaking
- 6) Not currently pregnant
- 7) Has no knowledge of infertility
- 8) Wanting to avoid pregnancy for at least a year (at least one person in the couple)
- 9) Not using a method of contraception at the moment OR only using low-efficacy or ineffective method of contraception (defined as using condom less than 100% of the time, Fertility-Awareness Based methods e.g., counting method, withdrawal method, spermicide, emergency contraception, and sponge)
- 10) Never used a non-reversible method (male or female sterilization)
- 11) Has sex in the past 3 months (woman)

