## Recruitment & Sampling

In each village, members of the Village Health Team (VHT) will assist our research staff in identifying potentially eligible couples. For the couples that we attempt to recruit based on the VHT's referral, the VHT will first independently visit couples' homes to introduce them to the study, and gain permission to return with the research assistant. If permission is granted, the VHT will accompany our research assistant to couples' homes to introduce our research assistant.

If both partners are together during this initial meeting, the research assistant will inform them of the overall study together, but will screen and assess eligibility separately, ensuring that participants are able to answer the eligibility screening questions about fertility preferences and current use of contraceptives in a private setting to ensure confidentiality. Research assistants will be trained in to try to separate spouses in a culturally appropriate and sensitive manner. In cases where the research assistant feels separate screening will not be possible, s/he will attempt to reschedule to come back and conduct the screenings separately. If a reschedule is not possible and screening must happen together, the research assistant will conduct a follow-up phone call or house visit with just the woman to confirm the accuracy of her responses. The research assistant will then obtain written informed consent from the participants. See recruitment script for eligibility screening questions. No identifying information will be collected for eligibility screening. The interviewer will proceed to conduct the baseline questionnaire after obtaining written informed consent for both partners.

If only one partner is present during the initial meeting, the research assistant will proceed with the eligibility screening. If the partner (male or female) is found eligible and interested, the research assistant will ask him/her to refer their partner to the study (either by calling their partner themselves, having the partner call the research assistant or the VHT). The research assistant will conduct the eligibility screening with the second partner over the phone, or will return to the house at the scheduled date and time, and follow the same procedures described above to assess eligibility, obtain informed consent for study participation, and conduct the baseline questionnaire.

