If an eligible participant is interested, but their partner declines participation, we will provide a referral to family planning services for a nearby clinic to the interested participant (in both the intervention and control villages to maintain balance between the study arms).

Enrolled couples can also refer other couples to the study (snowball sampling). They will provide the study contact to the referred couples directly, who can choose to contact the study team.

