## Data Analysis Plan

We assessed baseline equivalence between the study arms on demographics using Generalized Estimating Equation (GEE) models in SPSS v. 28, which account for dependence from repeated, dyadic data. We tested intercorrelations between variables that differed (p < 0.10) between arms at baseline, or variables deemed theoretically relevant (i.e., age, number of children), to identify covariates. Based on these analyses, all models controlled for religion (based on differences in baseline equivalence) and age. The time by intervention interaction on contraceptive uptake (main outcome) at follow-up was tested using GEE with a logit link distribution (couple the unit of analysis). We report unintended pregnancy descriptively (underpowered but included for feasibility). For all secondary outcomes, GEE was used (linear for continuous outcomes and logistic for binary outcomes), with time and gender specified as within-subject effects. Unstandardized betas (b) and standard errors (SE) are reported for continuous outcomes and adjusted odds ratios (AORs) and 95% confidence intervals (CIs) are reported for binary outcomes.

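### Arm appears to follow village, yet no stated model has a village or session-group level, so standard errors are too small if change is correlated within them

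*Combined protocol and SAP*

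**What the plan says.** No section describes how couples or villages came into an arm. The one relevant phrase is in Recruitment & Sampling: when a partner declines, the interested person is referred to family planning services "in both the intervention and control villages to maintain balance between the study arms". That treats the arms as two sets of villages. Inclusion criterion 3 ("Living within the selected villages in the last 3 months") and the way couples are found ("In each village, members of the Village Health Team (VHT) will assist our research staff in identifying potentially eligible couples") fit that reading. The same section lets enrolled couples refer others. Data management (Qualitative data) mentions recordings of group as well as individual counselling. Training of intervention facilitators describes group facilitators, and community leaders who lead discussions in session 3.

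The Data Analysis Plan is the only analysis text.

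- Its GEE models are introduced as ones "which account for dependence from repeated, dyadic data".
- For the main outcome, contraceptive uptake, the time-by-intervention interaction is "tested using GEE with a logit link distribution (couple the unit of analysis").
- Secondary outcomes use GEE "with time and gender specified as within-subject effects".
- For adjustment, "all models controlled for religion (based on differences in baseline equivalence) and age".

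Neither this section nor any other gives a village or session-group term, a number of villages, an ICC or a small-cluster correction.

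**The concern.** If whole villages are in one arm, the arm comparison is a comparison of villages. Couples in one village share local services, a Village Health Team, referral chains and possibly session groups, so their change over time may move together. A GEE that treats couples as independent counts each couple as a separate piece of evidence about the intervention. The standard error is then too small, the confidence interval too narrow and the p-value too low. With few villages, a local change unrelated to the intervention could be read as its effect and carried into the planning of a larger trial.

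**Working it through.** The plan states no sample size, power or ICC, so it has no figure to reproduce. What follows tests when the omission matters and shows its size over assumed ranges.

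**1. Inputs**

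| Input | Value | Source |
|---|---|---|
| Level of assignment | village | implied, Recruitment & Sampling |
| Couples per arm, n | 35 | assumed: Process Data gives 70 intervention participants for exit interviews, read as both partners of 35 couples; equal control arm assumed |
| Villages per arm, k | 2 or 4 | assumed |
| Test level | two-sided 5% | assumed; the plan mentions only 95% intervals |
| ICC of change, ρ | 0.01, 0.05, 0.10 | assumed |
| Test for secondary outcomes | time by arm | assumed; stated only for the main outcome |

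**2. What cancels.** Write a couple's outcome as a stable village level, plus a village-specific change, plus couple-level terms. In change from baseline the stable level drops out: exactly for a linear outcome with complete data, closely for a logit. The village-specific change stays. If secondary outcomes were instead tested by an overall arm effect, stable village differences would matter too.

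**3. Linear outcome.** With m = n/k couples per village, the variance of an arm's mean change is inflated by DE = 1 + (m − 1)ρ. A couple-level model omits DE, so actual type I error = 2 × [1 − Φ(1.96/√DE)]. Worked case, k = 2 and ρ = 0.05: m = 17.5; DE = 1 + 16.5 × 0.05 = 1.825; √DE = 1.35; 1.96/1.35 = 1.45; type I error 14.7%.

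| Setting | ρ = 0.01 | ρ = 0.05 | ρ = 0.10 |
|---|---|---|---|
| 2 villages per arm: √DE | 1.08 | 1.35 | 1.63 |
| type I error | 6.9% | 14.7% | 22.9% |
| 4 villages per arm: √DE | 1.04 | 1.18 | 1.33 |
| type I error | 5.9% | 9.6% | 14.1% |
| Session groups of 10 couples in both arms (assumed): √DE | 1.04 | 1.20 | 1.38 |
| type I error | 6.0% | 10.4% | 15.5% |

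At ρ = 0 the error is 5%. If 70 means couples, 2 villages per arm give 9.0, 23.3 and 35.0%. Simulation with the uncorrected robust standard error gives slightly more than the formula for 35 couples: 7.8, 16.1 and 25.2% (k = 2) and 6.6, 10.5 and 15.4% (k = 4), against 5.6-5.9% without clustering.

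**4. Logit outcome: which variation matters.** Null simulation with two visits, no covariates, log-odds −0.8 at baseline and 0 at follow-up, couple SD 1, GEE clustered on couple, 1,500 runs per setting, and 1 village (35 couples) or 2 villages (36 couples) per arm:

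- no village effect: 5.2% and 5.3%
- stable village effect only: 5.0% and 5.5%
- village variation in change, logit SD 0.42: 12.3% and 9.4%
- the same with SD 0.60: 19.2% and 12.7%

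A shorter run (600 trials) with 4 villages per arm showed no clear inflation: 6.7% with no village effect, 6.7% at SD 0.42 and 4.7% at SD 0.60.

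**5. Logit outcome: baseline use.** Null simulation with three visits, religion and age, 35 couples per arm, follow-up use 40% (50% when baseline is 30%), village differences at follow-up only, 10,000 trials per setting. Here the ICC is that of follow-up use. A value of 0.05 corresponds to an ICC of change of about 0.033-0.045, so this table does not line up with the one in step 3.

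| Villages per arm | ICC | 5% baseline use | 10-30% baseline use |
|---|---|---|---|
| 2 | 0.01 | 1.2% | 3.5-6.6% |
| 2 | 0.05 | 2.8% | 6.5-11.8% |
| 2 | 0.10 | 4.9% | 10.1-18.0% |
| 4 | 0.01 | 1.2% | 3.3-6.0% |
| 4 | 0.05 | 1.8% | 4.2-8.2% |
| 4 | 0.10 | 2.8% | 6.0-11.1% |

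Trials with an empty cell were excluded: about 31% at 5% baseline use, 5% at 10%, none at 20% or 30%. Without clustering the test rejects 0.8-0.9% at 5% baseline and 2.9-5.5% at 10-30%.

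**The case against.** The premise is thin. Assignment by village rests on one parenthesis. The plan does not name the subject variable of its GEE models, and a unit of analysis is not quite the same as a clustering level. No section says that control sessions were held in groups. The counts of 70 participants and 2 facilitators describe who is exit-interviewed, so they establish neither the size of the arm nor how many people delivered sessions. All of this stands, and it is why the size must be given as a conditional range and the fix made conditional on assignment by village.

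The main outcome is also the weakest case. Inclusion criterion 9 admits couples described as "Not using a method of contraception at the moment" or using only a low-efficacy method. If uptake means effective methods, which the plan does not define, baseline use may be near zero. The couple-level test is then below its nominal level in the 5% column above, and sparse cells are the larger problem. This stands too.

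Finally, this is a pilot and village-level tests have little power. That limits the weight of the point but does not answer it. The plan reports unintended pregnancy descriptively because it is underpowered, yet it tests uptake and reports standard errors and intervals for the other outcomes. Those have to suit the design. Low power is not mainly a cost of the village-level test either. For a 20-point difference in follow-up use, the couple-level logit test had only about 6-34% power in comparable simulations.

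A reader might infer that the trial's standard errors are wrong, or that a significant result for uptake would be a false positive. The documents do not support that: they do not show that change is correlated within village, or by how much.

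**Conclusion.** The concern holds as a conditional one. The plan names repeated measures and partners as its sources of dependence and leaves out the level at which arm appears to have been set. Followed as written, it understates uncertainty if, and only if, change is correlated within village or session group. Stable village differences do little harm to the interaction test. The consequence is clearest for continuous secondary outcomes: about 7-23% type I error with 2 villages per arm and 6-14% with 4. Those figures assume 35 couples per arm, a two-sided 5% level, a time-by-arm test and an ICC of change of 0.01 to 0.10. For the logit main outcome the direction itself depends on baseline use. The true size cannot be found from the documents. It should be fixed, because the remedy is cheap and the intervals cannot be interpreted without it.

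**What to change.** State the level at which arm was assigned, the number of villages and session groups in each arm, and the clustering level of every model. Then, if arm was set by village:

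- **Several villages per arm.** Base the tests on villages. Compare village mean change from baseline between arms with a t reference on villages minus 2 degrees of freedom. For partner-level outcomes, do this separately by gender or keep gender in the model. A mixed model with village variation in change, or a GEE clustered on village with a small-sample correction, is an alternative where the village count supports it. Account for session group where it differs from village.
- **Too few villages for that.** Keep the couple-level results, report a sensitivity range over plausible ICCs (for linear outcomes, multiply the standard error by √DE), and state that the intervals and p-values assume no village-level correlation in change.
- **One village per arm.** Report descriptive pilot estimates without tests and state that village and intervention effects cannot be separated.

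If couples were assigned individually, one sentence settles the village question and only session groups remain to be addressed.

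The cost is analysis work. Village should be known from recruitment; session-group membership may need compiling. The downside is wider intervals and fewer significant results. In simulation with 35 couples per arm, village-level intervals were 2.0-3.3 times as wide as couple-level ones with 4 villages in total and 1.2-1.6 times with 8. Power for a 20-point difference in follow-up use was 9-14% and 16-26%. A village-level comparison of uptake is on the risk-difference scale; the adjusted odds ratio can still be given descriptively.
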